### ***Contents of the abstinence bowl***

CTN will supply coded chits for use in recovery picks. There will be 500 chits supplied for the abstinence bowl. Fifty percent of the chits will say “good job” and will not result in an incentive award. 41.8% of the chits will result in a small incentive, 8% will result in a large incentive and only a very small percentage (0.2%) will result in a jumbo incentive. Chits should be placed on a table in the sequence drawn and remain there until all recovery picks are completed and data has been entered. Chit replacements can be obtained from national study coordinator should any be lost or damaged.

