### ***Escalating Schedule of recovery picks for primary drug abstinence***

Clients in the incentive group will earn at least one recovery pick for each sample submitted that tests negative for the primary drugs: cocaine, amphetamine, methamphetamine and provided a negative breath alcohol reading is obtained. The number of picks allowed at each

urine collection will escalate with consecutive week of negative testing on primary drugs. Specifically, an additional recovery pick is added for each consecutive week that the participant tests negative for cocaine, amphetamine, methamphetamine and alcohol.

Study week	Number of recovery picks for primary drug abstinence
1	1
2	2
3	3
4	4
5	5
etc	

Missing or positive samples result in reset to 1 in number of recovery picks for the next negative sample submitted.

The escalating schedule is designed to sustain long periods of abstinence, and as such, the highest rates of reinforcement are scheduled late in the protocol for continuously abstinent participants. In order to counteract discouragement from the low reinforcement rate expected early in the escalating draw protocol, a single \$20 bonus incentive will be given after two consecutive weeks of abstinence from primary target drugs. This bonus incentive can only be received once during the study; if a client re-sets and starts the escalating schedule over again, no bonus incentive will be available.

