### **Repeated measures variables**

For continuous variables that are measured either during treatment (e.g. at each follow-up time point), classical repeated measures analysis of variance would be possible if missing data is non-existent or minimal. If missing data is a problem, then methods of analysis used for mixed linear models will be used. These methods allow for missing data with repeated measures. For continuous or dichotomous variables measured at several time points (e.g. follow-up outcomes), we propose using GEE. GEE is a powerful analytic method that is used to correct for correlation among observations within subjects in a repeated measures design. Odds ratios and 95% confidence limits will be produced to represent differences between the treatment groups and to estimate the effects of other variables. It may be possible that there is decay over time in treatment effects. Focusing on only one time point (e.g. end-of-treatment), we propose to compare treatment and control groups using chi square and compute relative risk and 95% confidence limits. To adjust for covariates and possible site differences, logistic regression analysis will be used to assess treatment effects. While logistic regression provides accurate estimates of statistical significance, the method tends to produce inflated estimates of risk when prevalence of an outcome is high. Poisson regression may be used to produce more accurate estimates of risk relative risk).

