### 18.1 Risks

The risks of this study are minimal and are described below. Adverse events will be reported only for death, hospitalization and increase in gambling behavior, as defined below.

Dissatisfaction with study assignment. One risk is that participants randomly assigned to the no incentive condition will be dissatisfied with their assignment. This is a risk common to many randomized clinical trials, particularly where interventions cannot be blinded. The risk is explained as part of the consent procedure, and those unwilling to take the risk of assignment to control condition can refuse to participate. Experience of the Co-lead Investigator, who has conducted similar trials in community clinics, is that assignment dissatisfaction has not been a major problem.

Drug use following receipt of large prizes. Participants randomly assigned to the experimental incentive group will be able to earn small, large and jumbo incentive items under a variable ratio schedule as rewards for submitting drug-free urines. There is some risk that clients who have been abstinent would return to drug use following receipt of a large (\$20) or jumbo (\$80) prize. This is included as a risk due to concern that study patients may sell prize items and use the money to purchase drugs. The percentage of large and jumbo prize awards that are followed by drug use (i.e. a positive urine at the next study visit) will be reported, and compared if possible with return to drug observed on occasions when only small prizes or no prizes have been received. It should be noted that any detrimental effect of the protocol with regard to stimulating relapse is self-limiting, as clients can no longer earn incentives while actively using drugs.

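### Section 18.1 counts post-prize drug use per award but its comparator per occasion, so one urine can count several times and long-abstinent winners are over-weighted

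*Protocol*

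**What the plan says.** Under the risk of drug use after large prizes, Protocol section 18.1 describes a risk to people: "There is some risk that clients who have been abstinent would return to drug use following receipt of a large" or jumbo prize. The measure chosen for it is "The percentage of large and jumbo prize awards that are followed by drug use", where drug use means "i.e. a positive urine at the next study visit". This is to be "compared if possible with return to drug observed on occasions when only small prizes or no prizes have been received".

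Section 11.5 sets how prizes arise. Per pick, "8% will result in a large incentive and only a very small percentage (0.2%) will result in a jumbo incentive". The number of picks grows with abstinence: "an additional recovery pick is added for each consecutive week that the participant tests negative for cocaine, amphetamine, methamphetamine and alcohol". A missing or positive sample resets the count to one, and an opiate-negative urine adds two picks at each qualifying visit. Section 11.4 expects 24 urines per participant.

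Section 16.4 (Repeated measures variables) names GEE as a method "used to correct for correlation among observations within subjects in a repeated measures design". Section 18.1 does not refer to it.

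**The concern.** The prize side and the comparator side of this safety comparison use different units, and neither unit is the person.

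- **Shared urine.** If two or three large prizes are won at one visit, the single next urine enters the prize percentage two or three times. A visit without such a prize enters its next urine once.
- **Weighting.** Someone who stays abstinent makes more picks at every visit and has more qualifying visits, so contributes many awards that are not followed by use. Someone who uses again soon after a first large prize may contribute one.

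The percentage is therefore an average over awards that leans towards the participants least likely to use. The worry behind it is that prizes may be sold to buy drugs. A reader will naturally take the figure as a winner's risk, or take a figure below the comparator as evidence that prizes are harmless. It supports neither reading.

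**Working it through.** The protocol gives no expected value for this measure, so there is no figure of its own to reproduce.

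**Inputs from the protocol**
- Chance of a large or jumbo prize per pick: 0.08 + 0.002 = 0.082 (section 11.5).
- Picks per visit under continuous abstinence: 1 to 12 by week, plus 2 for an opiate-negative urine, so 3 to 14 (section 11.5).
- Visits: 24, two per week (section 11.4).

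**Step 1: how often one urine is shared.** With m picks, P(2 or more) = 1 − 0.918^m − m × 0.082 × 0.918^(m−1).

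| Picks m | P(at least one) | P(two or more) |
|---|---|---|
| 3 | 22.6% | 1.9% |
| 6 | 40.2% | 8.1% |
| 12 | 64.2% | 25.8% |
| 14 | 69.8% | 32.1% |

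Among 14-pick visits with any such prize, 32.1/69.8 = 46% have two or more.

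**Step 2: how awards accumulate in one person.** A continuous abstainer who is also opiate-negative makes 2 × (1 + … + 12) + 2 × 24 = 156 + 48 = 204 picks. Expected large or jumbo awards: 204 × 0.082 = 16.7. Expected visits with at least one: 2 × Σ(1 − 0.918^m) for m = 3 to 14 = 11.9. Without opiate picks the figures are 156 × 0.082 = 12.8 awards on 9.6 visits. A first negative visit with 3 picks yields 3 × 0.082 = 0.25 awards.

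**Step 3: effect on the percentages when prizes do nothing.** Assumptions, none given by the protocol: each participant has a fixed chance of a negative visit, drawn from Beta(0.6, 0.7) to Beta(2, 2); urines are opiate-negative half the time; prizes have no effect on use. Comparator visits are those that qualified for picks but brought no large or jumbo prize.

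| Measure | Positive at next visit |
|---|---|
| Per award (section 18.1) | 21-35% |
| Per visit with at least one award | 23-36% |
| Comparator visits | 33-41% |
| Winners, after first large or jumbo prize | 39-45% |

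- Moving from awards to visits adds about 1-2 points.
- A gap to the comparator remains after that move. Prize visits fall later in abstinent runs, where more picks are made. Comparing visits at the same number of picks brings the difference to about 0, which is the correct answer here.

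**Step 4: sensitivity**
- These Beta settings imply 46-50% negative urines, above the 20-35% that section 9 cites for methadone patients. At mean rates of 28-30% the pattern persists: 39-52% of awards against 55-61% of winners after their first prize.
- A second set of assumptions has 10% continuously abstinent, the rest 20-35% negative with or without persistence, and opiate picks always earned. It gives 14-35% per award, 16-39% per visit and 21-58% on comparator occasions. Counting visits adds about 1-5 points and leaves a gap of about 4-22 points.
- If everybody has the same chance of use, the per-award, per-visit and comparator figures agree (26.1%, 26.1%, 26.0%). The distortion needs participants to differ.

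**The case against.** The strongest reply is that the unit mismatch is nearly harmless. Counting visits moves the figure by only a point or two, and with identical participants it causes no bias at all. That stands: most of the gap to the comparator comes from when in an abstinent run prizes are won, so visit counting without matching on picks would still mislead.

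Three stronger conclusions are tempting, and the protocol supports none of them.
- **A few continuous abstainers dominate the percentage.** This depends on how many there are, which the protocol does not say. If 5% are continuously abstinent they hold 23-42% of awards; if 10%, 40-60%. Heavy over-weighting is secure; dominance is not.
- **The person-level relapse risk is understated.** Section 18.1 never offers the percentage as the share of winners who relapse. The 39-45% arises with no prize effect, so the gap reflects different weighting, not a hidden effect. That figure has no comparator and cannot show harm by itself.
- **The confidence interval will be too narrow.** Section 18.1 plans no interval or test.

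It can also be said that the measure is descriptive, that the comparison is conditional on being possible, and that the randomised comparisons of stimulant use (sections 16.1 and 16.3) capture the net effect of incentives without this weighting. All true, and they limit the importance. It might be added that derivation belongs in a statistical analysis plan. That does not remove the point, because section 18.1 itself fixes awards on one side and "observed on occasions when only small prizes or no prizes have been received" on the other. A plan that follows it inherits the mismatch.

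**Conclusion.** The point holds as a modest defect in a descriptive safety comparison. Two parts rest on the protocol alone: the units differ, and the pick schedule makes several awards share one next urine (32% of 14-pick visits; 16.7 awards on 11.9 visits for a continuous abstainer). The sizes rest on assumed differences between participants. Double counting lowers the figure by about 1-2 points, or 1-5 under the second set of assumptions. The weighting puts the per-award figure (21-35%) below the percentage of winners positive after their first large or jumbo prize (39-45%) even when prizes have no effect. The award percentage should be read neither as a winner's chance of returning to use nor, when it falls below the comparator, as reassurance.

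**What to change.** In section 18.1:
1. Count visits on both sides: visits with at least one large or jumbo prize, against visits that qualified for picks and brought only small prizes or none.
2. Compare them at the same number of picks, by stratifying or by a term in the model.
3. Use GEE clustered on participant, already named in section 16.4, and give 95% limits.
4. Report the percentage of winners who test positive at the visit after their first large or jumbo prize, labelled as descriptive because it has no comparator.

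The cost is a change of wording, a few variables derived from pick and urine results already recorded, and a little more analysis. The reported percentage will probably look less favourable than the award-based one.

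### The planned check for drug use after large prizes ignores the number of picks, so it will tend to understate harm if participants differ in their risk of use

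*Protocol*

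**What the plan says.** Protocol section 18.1, in the paragraph on drug use after large prizes, raises the worry that participants may sell $20 or $80 items and buy drugs. It then fixes a check. The share of large and jumbo awards with a positive urine at the following visit is to be given, and this figure is to be "compared if possible with return to drug observed on occasions when only small prizes or no prizes have been received". The outcome (a positive urine at the next visit) and both comparison groups are stated. Number of picks, length of abstinence and participant are not mentioned, and section 16 contains no analysis of this risk.

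Section 11.5 sets how prizes arise:

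- Bowl contents: "There will be 500 chits supplied for the abstinence bowl". Half of them carry no prize and 41.8% a small one. For the rest, the section says that "8% will result in a large incentive and only a very small percentage (0.2%) will result in a jumbo incentive".
- Escalation: "an additional recovery pick is added for each consecutive week that the participant tests negative for cocaine, amphetamine, methamphetamine and alcohol". A missing or positive sample resets the count to one.
- Opiate bonus: two further picks when the urine is also free of opiates.
- A one-off $20 bonus follows two consecutive abstinent weeks.

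Section 11.2, step 8, also lets clients choose a large incentive at intake.

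**The concern.** An occasion enters the large-prize group if at least one of its picks is large or jumbo. The more picks, the likelier that is, and the number of picks is set by prior abstinence and by that day's opiate result. Both plausibly predict the next urine. The two groups in section 18.1 therefore differ in prognosis before any prize is handed over. If longer abstinence goes with a lower chance of a positive next test, the large-prize group starts with the better prognosis and an adverse effect of the prize is diluted.

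For a safety check this is the unhelpful direction: a reassuring figure could reflect who wins large prizes and not what large prizes do. It is also the only analysis the protocol plans for this named risk.

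**Working it through.** **Bowl.** 500 × 50%, 41.8%, 8% and 0.2% gives 250, 209, 40 and 1 chits, which sum to 500. The stated composition is consistent. Chance of large or jumbo per pick: 8% + 0.2% = 8.2%.

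**Exposure by number of picks.** P(at least one large or jumbo in k picks) = 1 − 0.918^k.

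| Picks k | Example | Probability |
|---|---|---|
| 1 | first week or after reset, opiate-positive | 8.2% |
| 3 | first week, opiate-negative | 22.6% |
| 7 | fifth week, opiate-negative | 45.1% |
| 12 | twelfth week, opiate-positive | 64.2% |
| 14 | twelfth week, opiate-negative | 69.8% |

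Drawing without replacement (41 of 500 chits) changes little: 22.7% at 3 picks and 70.3% at 14. From 1 to 14 picks the probability rises 69.8/8.2 ≈ 8.5-fold. This step needs only the protocol's own rules.

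**Mechanism by hand (assumed risks, not an estimate of size).** Take equal numbers of occasions at 3 and 14 picks, next-visit positive risks of 40% and 10%, and no effect of the prize.

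- After large or jumbo: (0.226 × 0.40 + 0.698 × 0.10) / (0.226 + 0.698) = 17.3%.
- After small or none: (0.774 × 0.40 + 0.302 × 0.10) / (0.774 + 0.302) = 31.6%.

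The prize does nothing, yet the crude risk ratio is 17.3/31.6 = 0.55.

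**Size over the full schedule (simulation).** Taken from the protocol: 24 tests, the escalation and reset rules, two opiate bonus picks, 8.2% per pick. Assumed: 60% of urines opiate-negative; every urine given; each participant's chance of a positive test drawn from a symmetric beta distribution with mean 0.50 (none = constant 0.50, small = beta(5,5), moderate = beta(2,2), wide = beta(1,1)); a large or jumbo prize multiplies the next-visit risk by the true risk ratio (RR), capped at 1. The fixed awards are not modelled.

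| Differences between participants | Crude RR, true 1.00 | Crude RR, true 1.25 | Large-prize occasions in first two streak weeks (true 1.00) |
|---|---|---|---|
| None | 1.00 | 1.25 | 91% |
| Small | 0.96 | 1.20 | 82% |
| Moderate | 0.88 | 1.11 | 70% |
| Wide | 0.78 | 0.96 | 54% |

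A Mantel-Haenszel risk ratio stratified on picks gives about 1.00 and 1.24 to 1.25 in all four settings. Repeat runs move the crude values by about 0.01.

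**Second method.** An exact calculation on the odds-ratio scale (50% opiate-negative assumed), with a true odds ratio of 1.5, gives these crude values:

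- constant risk: 1.50
- mild differences between participants: 1.43
- risk falling 10%, 20% or 30% per abstinent week: 1.41, 1.24, 1.10
- marked differences: 0.99
- marked differences plus a 20% weekly fall: 0.76
- extreme differences: 0.71
- risk rising 5% per week: 1.56

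Stratified on picks, the odds ratio is 1.00 in every scenario without an effect and 1.35 to 1.50 when the truth is 1.5. The shortfall under strong differences is mainly non-collapsibility of the odds ratio.

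**Unit of count.** Section 18.1 counts awards on one side and occasions on the other, so an occasion with two large prizes counts twice. With marked differences and no effect, the positive percentage is 22.6% per award and 23.6% per occasion: a small shift, but avoidable.

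**The case against.** Section 18.1 names no estimator, does not exclude conditioning on picks, and qualifies the comparison with an if-possible clause. A statistical analysis plan not shown here could add the adjustment. That is fair, and it makes the fix a clarification. But the protocol does fix the outcome and the two groups, and those groups are not comparable under its own prize rules. The qualifier makes the comparison conditional, not valid.

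A reader might infer that large-prize occasions come mostly from long-abstinent participants, so that stable abstainers are set against early ones. That does not hold. In the settings with small to wide differences, 54% to 82% of large-prize occasions fall in the first two weeks of a streak, because early occasions far outnumber late ones. The mix shifts; the groups do not separate.

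A reader might also infer that the comparison is bound to hide harm. The documents do not support this either. The spread of risk between participants is not given, with constant risk there is no bias, and with risk rising over a streak it reverses slightly.

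Nor can it be said that the data already hold an unbiased answer for every large award. The intake incentive and the two-week $20 bonus are not drawn at random.

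Finally, the consequence is limited. This is neither a section 16 outcome nor a section 17 hypothesis. The randomised comparison of stimulant-negative urines captures the programme's net effect on stimulant use, though it cannot isolate single prizes.

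**Conclusion.** The point stands in a limited form. That exposure depends on the abstinence streak follows exactly from the protocol: 8.2% at 1 pick, 22.6% at 3, 69.8% at 14. The direction of bias needs one further assumption, plausible but not quantified in the protocol: that participants differ in their risk of use or that risk falls with abstinence. Under it the unadjusted comparison leans towards no harm. The usual result is attenuation; an effect disappears or reverses only when differences are marked. This is a secondary safety comparison, worth correcting because it is the only one planned for this risk and the remedy is nearly free.

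**What to change.** In Protocol section 18.1, state that return to use after drawn large or jumbo prizes will be compared with other pick occasions having the same number of picks at that visit. Use a Mantel-Haenszel risk ratio stratified on picks, or a GEE model with picks as a factor, in either case allowing for clustering by participant. Given the number of picks, which prize is drawn is random, so this uses randomisation the design already contains.

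Add three details:

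- The unit is the occasion, not the award.
- The intake large incentive and the two-week $20 bonus are left out of the drawn-prize exposure, or handled separately.
- The crude percentages are reported as description only.

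The cost is one or two sentences and slightly more analysis. Under section 11.5 software determines the number of picks and staff record the results, and section 11.4 schedules the next urine, so no new data are needed. Strata with many picks will be sparse, with some loss of precision.

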**Gambling behavior**

Days spent money on gambling in past 30 (state lottery included)

Amount of \$ spent on gambling in past 30 days

*Psychiatric symptoms:* Brief Symptom Inventory (BSI)

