Marked increase in gambling behavior. The variable ratio schedule proposed includes an element of chance, and there is some concern that this will stimulate gambling behavior in those who have a problem with this type of impulsive behavior. It should be noted that there is no evidence to support such a concern. Further, the variable ratio incentive procedure itself could not be defined as gambling. It does not require the volunteers to put up their own money, nor is there any chance that volunteers could benefit excessively or lose their own money as a result of participating successfully in the incentive program. There is a chance that an individual with a gambling problem in remission could be stimulated to resume gambling. For this reason, compulsive gambling in remission has been added as a study exclusion criteria. There is also a chance that individuals who tend to engage in excessive gambling and who abstain from drug use during the study would have more disposable income to spend on gambling. For this reason, gambling behavior will be monitored at study follow-up points. A substantial increase in self-reported gambling behavior at 1, 3 and 6 months compared with baseline will be reported as an adverse event. The changes needed to trigger an adverse event evaluation is an increase of 10 days or more per month on which gambling occurred (e.g. from 10 to 20 days), a 50% or greater increase in the reported amount of money spent on gambling and an absolute amount spent of at least \$100 per month. Any subject who meets these criteria will be given a clinical interview regarding their gambling behavior in relation to other changes in life circumstances. The adverse event report will include a judgement by the clinician regarding the extent to which the behavior change might have been protocol-related. Information about gambling behaviors reported by study subjects will be provided to counselors so that they can work on this independent behavior problem with their clients, as appropriate. Subjects may be withdrawn from the study protocol and referred for specialized gambling treatment if clinically indicated.

Hospitalization. An adverse event will be reported for any hospitalization episode. Drug overdose requiring medical intervention will be tracked separately. Overdose is a serious risk among drug abusers in general, but may be of particular concern when patients have abstained for any substantial period of time.

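### The gambling adverse-event trigger in Protocol 18.1 cannot fire for a participant who gambles on 21 or more of 30 days at baseline, however much spending rises

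*Protocol*

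**What the plan says.** Protocol 18.1 opens by limiting adverse-event reports to death, hospitalization and a gambling increase as that section defines it. Under the heading on marked increases in gambling it then states: "A substantial increase in self-reported gambling behavior at 1, 3 and 6 months compared with baseline will be reported as an adverse event".

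The next sentence lists what is needed, beginning with: "an increase of 10 days or more per month on which gambling occurred (e.g. from 10 to 20 days), a 50% or greater increase". The percentage applies to reported gambling expenditure, and a third condition, joined by *and*, sets a floor of $100 a month on that expenditure. The text continues: "Any subject who meets these criteria will be given a clinical interview". The adverse-event report also carries a clinician's judgement on whether the change was related to the protocol.

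The same paragraph gives a reason for monitoring, which is the possibility of extra money for gambling: "individuals who tend to engage in excessive gambling and who abstain from drug use during the study would have more disposable income to spend on" it.

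Section 14 (Gambling behavior) defines the two measurements. One is "Days spent money on gambling in past 30 (state lottery included"). The other is the dollar amount "spent on gambling in past 30 days".

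Section 8 excludes people in recovery from gambling, meaning those who stopped because of earlier problems. It does not exclude people who gamble now.

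**The concern.** The day condition is an absolute rise on a scale that stops at 30. Joined by *and* to the money conditions, it becomes a gate that the most frequent gamblers cannot pass. They are the people, and money is the route, that 18.1 names when it explains why gambling is monitored.

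For these participants a steep rise in spending would lead to no adverse-event report, no triggered clinical interview and no recorded judgement of relatedness. Because 18.1 ties gambling adverse events to this definition alone, no other adverse-event route picks them up. Lottery play counts as a gambling day, so a baseline above 20 days is possible even in someone whose stakes are small.

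**Working it through.** **Inputs**

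- Day condition: follow-up days minus baseline days ≥ 10 (18.1).
- Money conditions: follow-up spending ≥ 1.5 × baseline spending, and follow-up spending ≥ $100 per month (18.1).
- Both items cover the past 30 days (Section 14), so days run from 0 to 30.
- Each follow-up at 1, 3 and 6 months is compared with baseline (18.1).

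**How the conditions combine.** The three items are listed as the changes needed, the last is joined by *and*, and the following sentence speaks of meeting the criteria in the plural. All three together is the natural reading. A reading in which any one suffices is implausible, because $100 a month with no change from baseline would then count as an increase. The text never says *all of*, however.

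**The protocol's own example.** 10 to 20 days is a rise of 20 − 10 = 10, which meets the day condition.

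**The ceiling.** For baseline b the largest possible rise is 30 − b. The day condition needs 30 − b ≥ 10, so b ≤ 20.

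| Baseline days | Largest possible rise | Day condition reachable? |
|---|---|---|
| 10 | 20 | yes |
| 20 | 10 | yes, only by reaching 30 |
| 21 | 9 | no |
| 25 | 5 | no |
| 30 | 0 | no |

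The trigger in 18.1 is worded per month and the item per 30 days. With a 28-day window the last reachable baseline is 18, and with a 31-day window it is 21. The ceiling moves by a few days but does not disappear.

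**Illustrative cases.** The dollar amounts, and all the day counts other than the protocol's own 10-to-20 example, are assumptions.

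| Days | Spending | Rise in days | Spending ratio | Trigger met? |
|---|---|---|---|---|
| 10 to 20 | $70 to $105 | 10 | 105/70 = 1.5 | yes |
| 20 to 30 | $200 to $300 | 10 | 300/200 = 1.5 | yes |
| 21 to 30 | $200 to $2,000 | 9 | 2,000/200 = 10 | no |
| 25 to 30 | $100 to $3,000 | 5 | 3,000/100 = 30 | no |

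The last two rows meet both money conditions by a wide margin and fail only on days.

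**Zero baseline spending.** The percentage rise divides by baseline spending and is undefined at $0. This does not affect the ceiling group, because a gambling day is a day on which money was spent. It affects people who start gambling during the study, and 18.1 gives no rule for them.

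**The case against.** **The trial still measures gambling.** A reader might infer that the trial as a whole would understate gambling harm. The documents do not support that. Gambling is recorded in both arms at intake and at 1, 3 and 6 months, days gambled is a listed follow-up outcome (16.3), and 17.4 carries a between-group hypothesis on gambling measures. Participants who cannot trip the trigger still count in those comparisons. One reservation stands: 16.3 lists days but not the amount spent, although Section 14 collects it.

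**Individual safeguards remain.** Under 18.1 counselors receive gambling information whether or not the trigger is met, and withdrawal or referral depends on clinical indication. This stands, but neither is an adverse-event report.

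**A threshold is not a contradiction.** A reader might also fault the rule for missing rises such as 0 to 9 or 10 to 19 days. That is what any 10-day threshold does, and a sponsor may define what counts as substantial. The ceiling is different: from 21 days upward no outcome can qualify.

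**Requiring several conditions has a purpose.** If days alone or money alone sufficed for everyone, ten days of $1 lottery tickets (10 × $1 = $10) would start an evaluation. So would $67 rising to $101 (101/67 = 1.51) with no change in days. This is a fair argument against loosening the rule for all participants. It does not defend a rule that cannot fire for some of them.

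**The wording is loose.** The sponsor may have meant another combination. If so, the text should say so, since sites could otherwise apply it differently.

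**Conclusion.** The point holds in a limited form. On the plain reading of 18.1 and the 30-day item in Section 14, any participant with 21 or more gambling days at baseline is outside the gambling adverse-event definition whatever happens to spending. This conflicts with the purpose that 18.1 itself states.

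The boundary is exact arithmetic. It rests on two things: that all three conditions are required, and that the month in 18.1 is the 30-day recall window in Section 14. The number of participants affected cannot be given, because the protocol reports no baseline distribution of gambling days.

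The consequence is confined to adverse-event reporting and the evaluation that follows it. No primary outcome is touched, and the between-arm comparison of gambling is unaffected. The correction should be made, but the trial's conclusions on efficacy do not depend on it.

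**What to change.** In 18.1:

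1. State explicitly how the three conditions combine.
2. Reconcile the trigger with the 30-day scale and the stated reason for monitoring, so that it can fire for participants whose baseline days leave no room for a 10-day rise. One way, using only the protocol's existing figures, is to let the two spending conditions suffice for reporting in that group. The rule for everyone else stays as it is.
3. State how the percentage rise is handled when baseline spending is zero.
4. Use the same window in the trigger and in the questionnaire item.

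In the gambling analysis, tabulate change in days and change in amount spent by arm, since 16.3 names only days.

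The cost is a wording change and one table. Both items are already collected at intake and at the 1-, 3- and 6-month follow-ups, so no new data are needed. The downside is some additional adverse-event evaluations. Under the example in step 2, a participant at 25 days whose spending goes from $70 to $105 would be evaluated. The extra workload is limited to those with 21 or more baseline days, plus any newly covered by the zero-spending rule. It should be small, though the documents give no figure from which to estimate it.
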